4.3.2.1 Atezolizumab and Atezolizumab Placebo

Atezolizumab 840 mg or placebo will be administered by IV infusion on Days 1 and 15 of Cycle 1 and Days 1 and 15 (every 2 weeks) of subsequent cycles (see [Table 2](#) in Section 3.1 for a summary of the treatment regimens).

Administration of atezolizumab will be performed in a setting with medical facilities and staff who are trained to monitor for and respond to medical emergencies. For anaphylaxis precautions, see [Appendix 6](#).

No premedication will be allowed for the first dose of atezolizumab. Patients who experience an infusion-related reaction with the first infusion may receive premedication with antihistamines or antipyretics or analgesics (excluding acetaminophen; see Section [4.4.2](#)) for subsequent infusions.

The initial dose of atezolizumab will be administered over 60 (± 15) minutes. Subsequent infusions will be administered over 30 (± 10) minutes if the previous infusion was tolerated without infusion-associated adverse events, or 60 (± 15) minutes if the patient experienced an infusion-associated adverse event with the previous infusion. Vital signs are to be measured before, as well as during, and after infusions, if clinically indicated, as outlined in Section [4.5.4](#).

Guidelines for medical management of infusion-related reactions are provided in [Appendix 10](#).

No dose modification for atezolizumab is allowed. Guidelines for treatment interruption or discontinuation are provided in Section [5.1.5.4](#) and [Appendix 10](#).

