5.1.1 Risks Associated with Atezolizumab

Atezolizumab has been associated with risks such as the following: infusion-related reactions and immune-mediated hepatitis, pneumonitis, colitis, pancreatitis, diabetes mellitus, hypothyroidism, hyperthyroidism, adrenal insufficiency, hypophysitis, Guillain-Barré syndrome, myasthenic syndrome or myasthenia gravis, *facial paresis*, *myelitis*, meningoencephalitis, myocarditis, *pericardial disorders*, nephritis, myositis, and severe cutaneous adverse reactions. *In addition*, immune-mediated reactions may involve any organ system and lead to hemophagocytic lymphohistiocytosis. Refer to Appendix 10 of the protocol and to Section 6 of the Atezolizumab Investigator's Brochure for a detailed description of anticipated safety risks for atezolizumab.

Guidelines for management of patients who develop specific adverse events associated with atezolizumab, vemurafenib, or cobimetinib are provided in Section 5.1.5.4 (see Table 3), and guidelines for events associated only with atezolizumab are provided in Appendix 10.

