5.1.5.4 Management Guidelines

In general, toxicities should be managed with supportive care, dose modifications (if applicable), and treatment interruptions applied to the component of the study treatment judged to be the primary cause. Additional tests or procedures, such as autoimmune serology or biopsies to obtain tissue samples, may be performed to determine a possible immunogenic etiology. Patients should be monitored closely upon initiation of the third treatment component on Days 1 and 15 of Cycle 1 and Cycle 2, as well as the days immediately following these visits. Regular telephone contact and, if needed, unscheduled laboratory tests are strongly recommended.

Guidelines for management of patients who experience cobimetinib, vemurafenib, and atezolizumab specific adverse events are provided in [Table 3](#). The table also includes general guidelines for dose modifications and treatment delays and discontinuation. The guidelines in [Table 3](#) are not intended to replace clinical judgment or dictate care of individual patients.

Guidelines for management of cobimetinib and vemurafenib toxicities in [Table 3](#) will not apply to reversible laboratory abnormalities with no clinical sequelae or no clinical significance as determined by the investigator in consultation with the Medical Monitor.

Risks associated with atezolizumab and guidelines for the management of adverse events associated with atezolizumab are provided in Section 5.1.1 and [Appendix 10](#).

Table 3 Guidelines for Management of Patients Who Experience Specific Adverse Events

Event	Action to Be Taken

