- ^d Patients on a cobimetinib dose less than 60 mg will reduce by one dose level reduction (a 20-mg daily reduction), from a 40-mg daily dose to a 20-mg daily dose, and patients on a 20-mg daily dose at the time of the interruption (for LVEF decline) should discontinue cobimetinib.

Table 3 Guidelines for Management of Patients Who Experience Specific Adverse Events (cont.)

Event	Action to Be Taken
Rhabdomyolysis or CPK elevation	
General guidance	
 Consider withholding cobimetinib while investigating etiology. Continue atezolizumab and vemurafenib. Assess patient for any history of strenuous physical activity, blunt trauma, or recent intramuscular injections. Evaluate for cardiac injury and rhabdomyolysis. If evidence of clinically significant cardiac injury or rhabdomyolysis, consider permanent discontinuation of cobimetinib.
Asymptomatic CPK elevation, Grade 1, 2, or 3	
 Continue all study treatment.
Rhabdomyolysis or symptomatic CPK elevation, Grade 1, 2, or 3	
 Withhold cobimetinib. Continue atezolizumab and vemurafenib. If event improves by at least one grade within 28 days, resume cobimetinib with dose reduced by one level. If not, permanently discontinue cobimetinib.
Rhabdomyolysis or CPK elevation (symptomatic or asymptomatic), Grade 4	
 Withhold cobimetinib. Continue atezolizumab and vemurafenib. If event improves to Grade ≤ 3 within 28 days, resume cobimetinib with dose reduced by one level. If not, permanently discontinue cobimetinib.
Grade 3 or 4 or intolerable Grade 2 treatment-related toxicities not described above	
 Withhold all study treatment. If event resolves to Grade 1 or better within 12 weeks, resume atezolizumab at fixed dose. If not, permanently discontinue atezolizumab.^{a,b,c} If event resolves to Grade 1 or better within 28 days, resume cobimetinib and vemurafenib with doses reduced by one level. If not, permanently discontinue cobimetinib and vemurafenib.

CPK = creatine phosphokinase.

^a If corticosteroids have been initiated, they must be tapered over ≥ 1 month to ≤ 10 mg/day oral prednisone or equivalent before atezolizumab can be resumed.

^b Atezolizumab may be withheld for a period of time beyond 12 weeks to allow for corticosteroids to be reduced to ≤ 10 mg/day oral prednisone or equivalent.

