Patients may present with signs and symptoms of sensory and/or motor neuropathy. Diagnostic work-up is essential for an accurate characterization to differentiate between alternative etiologies. Management guidelines for neurologic disorders are provided in Section [5.1.5.4](#) with specific guidelines for myelitis provided in [Table 3](#).

IMMUNE-MEDIATED MENINGOENCEPHALITIS

Immune-mediated meningoencephalitis should be suspected in any patient presenting with signs or symptoms suggestive of meningitis or encephalitis, including, but not limited to, headache, neck pain, confusion, seizure, motor or sensory dysfunction, and altered or depressed level of consciousness. Encephalopathy from metabolic or electrolyte imbalances needs to be distinguished from potential meningoencephalitis resulting from infection (bacterial, viral, or fungal) or progression of malignancy, or secondary to a paraneoplastic process.

All patients being considered for meningoencephalitis should be urgently evaluated with a CT scan and/or MRI scan of the brain to evaluate for metastasis, inflammation, or edema. If deemed safe by the treating physician, a lumbar puncture should be performed and a neurologist should be consulted.

Patients with signs and symptoms of meningoencephalitis, in the absence of an identified alternate etiology, should be treated according to the guidelines in Section [5.1.5.4](#).

Appendix 10
Risks Associated with Atezolizumab
and Guidelines for Management of Adverse Events Associated
with Atezolizumab (cont.)

RENAL EVENTS

Eligible patients must have adequate renal function. Renal function, including serum creatinine, should be monitored throughout study treatment. Patients with abnormal renal function should be evaluated and treated for other more common etiologies (including prerenal and postrenal causes, and concomitant medications such as non-steroidal anti-inflammatory drugs). Refer the patient to a renal specialist if clinically indicated. A renal biopsy may be required to enable a definitive diagnosis and appropriate treatment.

Patients with signs and symptoms of nephritis, in the absence of an identified alternate etiology, should be treated according to the guidelines in [Table 4](#).

Table 4 Management Guidelines for Renal Events

Event	Management

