Renal event, Grade 1	
Continue atezolizumab.Monitor kidney function, including creatinine and urine protein, closely until values resolve to within normal limits or to baseline values.
Renal event, Grade 2	
Withhold atezolizumab for up to 12 weeks after event onset.^aRefer patient to renal specialist.Initiate treatment with corticosteroids equivalent to 1–2 mg/kg/day oral prednisone.If event resolves to Grade 1 or better, resume atezolizumab.^bIf event does not resolve to Grade 1 or better while withholding atezolizumab, permanently discontinue atezolizumab and contact Medical Monitor.^c

^a Atezolizumab may be withheld for a longer period of time (i.e., > 12 weeks after event onset) to allow for corticosteroids (if initiated) to be reduced to the equivalent of ≤ 10 mg/day oral prednisone. The acceptable length of the extended period of time must be based on *the investigator's* benefit–risk *assessment* and in alignment with the protocol requirements for the duration of treatment and documented by the investigator. The Medical Monitor is available to advise as needed.

^b If corticosteroids have been initiated, they must be tapered over ≥ 1 month to the equivalent of ≤ 10 mg/day oral prednisone before atezolizumab can be resumed.

^c Resumption of atezolizumab may be considered in patients who are deriving benefit and have fully recovered from the immune-mediated event. The decision to re-challenge patients with atezolizumab should be based on *the investigator's* benefit–risk *assessment* and documented by the investigator. The Medical Monitor is available to advise as needed.

Appendix 10
Risks Associated with Atezolizumab
and Guidelines for Management of Adverse Events Associated
with Atezolizumab (cont.)

Table 4 Management Guidelines for Renal Events (cont.)

Event	Management
Renal event, Grade 3 or 4	
• Permanently discontinue atezolizumab and contact Medical Monitor.• Refer patient to renal specialist and consider renal biopsy.• Initiate treatment with corticosteroids equivalent to 1–2 mg/kg/day oral prednisone.• If event does not improve within 48 hours after initiating corticosteroids, consider adding an immunosuppressive agent.• If event resolves to Grade 1 or better, taper corticosteroids over \geq1 month.

IMMUNE-MEDIATED MYOSITIS

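### Table 3's catch-all row and Appendix 10 give opposite atezolizumab defaults for Grade 3–4 nephritis of shared or uncertain cause that recovers within 12 weeks

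*Protocol*

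**What the plan says.** Table 3 in Section 5.1.5.4 lists actions by event and includes a residual row for "Grade 3 or 4 or intolerable Grade 2 treatment-related toxicities not described above". That row withholds all study treatment and then says "If event resolves to Grade 1 or better within 12 weeks, resume atezolizumab at fixed dose"; otherwise atezolizumab is stopped for good. The visible table has no row for nephritis or raised creatinine.

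Appendix 10 has its own renal section. It reads "Patients with signs and symptoms of nephritis, in the absence of an identified alternate etiology, should be treated according to the guidelines" in Table 4 of that appendix. The Grade 3 or 4 row there tells the site to "permanently discontinue atezolizumab and contact Medical Monitor", with no re-challenge footnote attached to that row.

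Four other places bear on which text a site should follow:

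- Section 5.1.5.4 says that "guidelines for the management of adverse events associated with atezolizumab are provided in Section 5.1.1" and Appendix 10, and that modifications apply to the component judged to be the main cause.
- Section 5.1.1 sends events associated with any of the three drugs to Table 3, and says that "guidelines for events associated only with atezolizumab are provided in Appendix 10".
- Section 4.3.2.1, on atezolizumab, says "Guidelines for treatment interruption or discontinuation are provided in Section" 5.1.5.4 and Appendix 10, without ranking them.
- Sections 1.5.3 and 5.1.3.11 name nephritis as a possible overlapping toxicity of the triplet and report interstitial nephritis with vemurafenib.

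**The concern.** For one serious toxicity that the protocol itself anticipates, two tables give different default actions for the same drug, and neither row mentions the other. A site that reads the catch-all literally takes the less cautious course and restarts atezolizumab. A site that follows the renal section of Appendix 10 stops it.

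Sites have a practical reason to open the catch-all. Table 4 of Appendix 10 gives only the atezolizumab action. Section 5.1.3.11 names kidney-injury dose guidance for vemurafenib, but no separate set is visible. The catch-all is therefore the visible instruction for cobimetinib and vemurafenib, and the atezolizumab restart stands in the same cell. Investigators are also blinded to arm (Section 4.2) yet must judge causality drug by drug (Section 5.3.4), so deciding that an event belongs to atezolizumab alone is not easy.

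The stake is consistent safety management, not inference.

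**Working it through.** No arithmetic beyond counting applies; the check sets the texts side by side.

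**Step 1: where the two atezolizumab defaults differ.** Table 3's footnotes and the Grade 2 row of Table 4 both allow the hold to run past 12 weeks for a steroid taper.

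| Treatment-related nephritis, no other etiology identified | Table 3 catch-all | Appendix 10, Table 4 | Same end point? |
|---|---|---|---|
| Intolerable Grade 2, Grade 1 or better within 12 weeks | Hold, then resume | Hold, then resume | Yes |
| Intolerable Grade 2, not recovered | Hold, then stop | Hold, then stop | Yes |
| Grade 3–4, not recovered within 12 weeks | Hold, then stop | Stop at once | Yes; no further doses either way |
| Grade 3–4, Grade 1 or better within 12 weeks | Hold, then resume at fixed dose | Stop at once | **No** |

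Only the last line conflicts.

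**Step 2: does the routing text settle that line?**

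- Toward Table 4: the renal section of Appendix 10 is directive, and Section 5.1.5.4 points atezolizumab-associated events to Appendix 10.
- Toward Table 3: Section 5.1.1 keeps Appendix 10 for atezolizumab-only events, and Sections 1.5.3 and 5.1.3.11 show that nephritis is not one.
- Neutral: Section 4.3.2.1 cites both.

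No visible sentence says which prevails.

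**Step 3: how the two sources divide the work.**

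- Appendix 10 sends 8 groups back to Section 5.1.5.4: pulmonary, hepatic, gastrointestinal, endocrine other than hypophysitis, ocular, pancreatic, dermatologic and neurologic.
- It prints its own table for 6: hypophysitis, cardiac, infusion-related reactions with cytokine release syndrome, renal, myositis, and the hemophagocytic/macrophage syndromes. Renal is among these, which supports Table 4 as the intended source.
- Of those 6, Table 3 visibly hands over 1 (infusion-related reactions) by an explicit row. Renal has none.
- Section 1.5.3 lists 8 overlapping toxicities. Seven have a visible Table 3 entry (gastrointestinal, liver, dermatologic, pancreatitis, hyperglycemia, ocular, pneumonitis); 8 − 7 = 1, nephritis or raised creatinine, does not.

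**Step 4: test the label on another event.** The hemorrhage rows are printed after the catch-all. Read by position, treatment-related Grade 3–4 hemorrhage is also not described above it. The catch-all would then withhold all study treatment, whereas the Grade 3 hemorrhage row keeps atezolizumab going, and the Grade 4 row continues it subject to clinical indication. The label therefore misfires inside its own table, whatever one concludes about Appendix 10.

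**The case against.** The case for leaving the text alone is substantial. Modifications follow the component judged the primary cause: nephritis attributed to atezolizumab goes to Appendix 10, and kidney injury attributed to vemurafenib goes to vemurafenib guidance. On a natural reading, a vemurafenib cause is an alternate etiology, so Table 4 drops out and there is no clash. Appendix 10 also confines its general advice to events not covered in its own subsections, which shows that specific text is meant to prevail, at least there. A strictly positional reading defeats the hemorrhage rows and would set the catch-all against the Appendix 10 stops for myocarditis and suspected hemophagocytic syndrome; a sensible site would not read it that way. Table 3's guidelines "are not intended to replace clinical judgment or dictate care of individual patients", and Appendix 10 lets an investigator consider restarting atezolizumab in a recovered patient who is benefiting. Both routes can thus end in resumption. Finally, Section 5.1.4 on combination use is blacked out and might carry a pointer.

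Most of this stands, and it narrows the point. It does not remove it. Attribution does not decide nephritis of shared or indeterminate cause, which is where Section 5.1.1 pulls away from Appendix 10. Discretionary re-challenge makes restarting a documented exception; the catch-all makes it the rule. The hemorrhage example is better taken as evidence that the label is badly worded than as a reason to ignore it.

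A reader might infer that the protocol directs sites to restart atezolizumab after severe nephritis, or gives no guidance on which table to use. The documents support neither: restarting requires recovery within 12 weeks, and the renal section of Appendix 10 is a plain direction to Table 4. Nor do they support reading Table 4 as an absolute bar. For pneumonitis, Table 3 adds a footnote against restarting after a permanent stop; the renal rows have none.

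**Conclusion.** Wrong as written, minor. The written defaults conflict for Grade 3–4 nephritis of shared or indeterminate cause, without an identified alternate etiology, that reaches Grade 1 or better within 12 weeks. The structure favours stopping, but no visible sentence says so, and the literal text of the catch-all gives the less cautious action. The same label literally contradicts the hemorrhage rows.

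The documents give no incidence for this group, so no number of patients is claimed. Type I error, power and the endpoints are untouched. The conclusion rests on the visible text: it assumes that neither the redacted part of Table 3 nor Section 5.1.4 contains a renal row or a precedence statement, which cannot be verified.

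**What to change.** 1. Relabel the catch-all so that its closing words read: *not described elsewhere in this table or, for atezolizumab, in Appendix 10*. This cures the nephritis and hemorrhage readings together.
2. Add one sentence under Table 3: Appendix 10 governs the atezolizumab action for the events it lists, and the existing cobimetinib and vemurafenib instructions are unchanged.
3. Optionally, add a renal row to Table 3 that refers to Appendix 10, in the form already used for infusion-related reactions, with its clinical content left to the sponsor.

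The cost is protocol wording only: one label, one sentence and, if wanted, one cross-reference row. It adds no procedures, visits or staff.

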5.2 SAFETY PARAMETERS AND DEFINITIONS

Safety assessments will consist of monitoring and recording adverse events, including serious adverse events and [REDACTED], performing protocol-specified safety laboratory assessments, measuring protocol-specified vital signs, and conducting other protocol-specified tests that are deemed critical to the safety evaluation of the study.

Certain types of events require immediate reporting to the Sponsor, as outlined in Section [5.4](#).

5.2.1 Adverse Events

According to the ICH guideline for Good Clinical Practice, an adverse event is any untoward medical occurrence in a clinical investigation subject administered a pharmaceutical product, regardless of causal attribution. An adverse event can therefore be any of the following:

- Any unfavorable and unintended sign (including an abnormal laboratory finding), symptom, or disease temporally associated with the use of a medicinal product, whether or not considered related to the medicinal product
- Any new disease or exacerbation of an existing disease (a worsening in the character, frequency, or severity of a known condition), except as described in Section [5.3.5.10](#)
- Recurrence of an intermittent medical condition (e.g., headache) not present at baseline
- Any deterioration in a laboratory value or other clinical test (e.g., ECG, X-ray) that is associated with symptoms or leads to a change in study treatment or concomitant treatment or discontinuation from study drug
- Adverse events that are related to a protocol-mandated intervention, including those that occur prior to assignment of study treatment (e.g., screening invasive procedures such as biopsies)

5.2.2 Serious Adverse Events (Immediately Reportable to the Sponsor)

A serious adverse event is any adverse event that meets any of the following criteria:

- Is fatal (i.e., the adverse event actually causes or leads to death)
- Is life threatening (i.e., the adverse event, in the view of the investigator, places the patient at immediate risk of death)

This does not include any adverse event that had it occurred in a more severe form or was allowed to continue might have caused death.

[figure not shown]
- Requires or prolongs inpatient hospitalization (see Section [5.3.5.11](#))

- Results in persistent or significant disability/incapacity (i.e., the adverse event results in substantial disruption of the patient's ability to conduct normal life functions)
- Is a congenital anomaly/birth defect in a neonate/infant born to a mother exposed to study drug
- Is a significant medical event in the investigator's judgment (e.g., may jeopardize the patient or may require medical/surgical intervention to prevent one of the outcomes listed above)

The terms "severe" and "serious" are not synonymous. Severity refers to the intensity of an adverse event (e.g., rated as mild, moderate, or severe, or according NCI CTCAE; see Section 5.3.3); the event itself may be of relatively minor medical significance (such as severe headache without any further findings).

Severity and seriousness need to be independently assessed for each adverse event recorded on the eCRF.

Serious adverse events are required to be reported by the investigator to the Sponsor immediately (i.e., no more than 24 hours after learning of the event; see Section 5.4.2 for reporting instructions).

• • • • •

• • • • •

• 8

5.3 METHODS AND TIMING FOR CAPTURING AND ASSESSING SAFETY PARAMETERS

The investigator is responsible for ensuring that all adverse events (see Section 5.2.1 for definition) are recorded on the Adverse Event eCRF and reported to the Sponsor in accordance with instructions provided in this section and in Sections 5.4–5.6.

For each adverse event recorded on the Adverse Event eCRF, the investigator will make an assessment of seriousness (see Section 5.2.2 for seriousness criteria), severity (see Section 5.3.3), and causality (see Section 5.3.4).

5.3.1 Adverse Event Reporting Period

Investigators will seek information on adverse events at each patient contact. All adverse events, whether reported by the patient or noted by study personnel, will be recorded in the patient's medical record and on the Adverse Event eCRF.

After informed consent has been obtained **but prior to initiation of study treatment**, only serious adverse events caused by a protocol-mandated intervention (e.g., invasive procedures such as biopsies, discontinuation of medications) should be reported (see Section 5.4.2 for instructions for reporting serious adverse events).

After initiation of study treatment, adverse events will be reported as follows:

- All adverse events will be reported until 30 days after the final dose of study treatment or until initiation of subsequent anti-cancer therapy, whichever occurs first
- Serious adverse events and [REDACTED] will continue to be reported until 90 days after the final dose of study treatment or until initiation of subsequent anti-cancer therapy, whichever occurs first.
- All new primary neoplasms (benign or malignant), including new primary melanoma, will be reported until 6 months after the final dose of vemurafenib. Any new primary malignant neoplasm other than cutaneous squamous cell carcinoma should be reported as a serious adverse event.

